Call to Door Timing in Out-of-hospital Cardiac Arrest

Study Protocol

Version No: 1.0.0

Document Date: May 1, 2023

NCT05724914

Table of Contents

1. Background	3
2. Methods	4
3. Statistical Analysis Plan	5

1. Background

Out-of-hospital cardiac arrest (OHCA) remains a significant global health challenge, with survival rates showing modest improvement but still remaining low. The chain of survival, including early recognition, initiation of CPR, rapid defibrillation, and effective advanced life support, is crucial for improving survival rates in sudden cardiac arrest cases. Efforts to reduce emergency medical services (EMS) response times have been instrumental in enhancing survival rates during the pre-pandemic period.

Recent studies have revealed that the coronavirus disease 2019 (COVID-19) pandemic has adversely affected EMS response times, potentially leading to delayed treatment for patients with OHCA. This has coincided with a sharp increase in OHCA mortality during the COVID-19 pandemic era. However, there is a lack of data regarding the clinical implications of the time delay from first emergency call to hospital arrival on the prognosis of OHCA patients. Therefore, this study aims to investigate the impact of time from call to hospital arrival (CtD time) on clinical outcomes in patients experiencing OHCA.

2. Methods

2.1. Patients: Patients will be recruited from The Korea OHCA registry

2.2. Time of recruitment: January 1, 2016 – December 31, 2021

2.3. Inclusion criteria: Patients of out-of-hospital cardiac arrest were reported to The Korea OHCA Registry

2.4. Exclusion criteria:

- Non-cardiac origin (external cause including asphyxia, hanging, fall, drowning, traffic injury and drug overuse, respiratory, non-traumatic bleeding, malignancy, brain hemorrhage, other disease, unknown)
- Under 18 years of age
- Patients who did not receive any CPR
- Missing data

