2.6. Hypothesis

- 1) The study hypothesizes that a delayed time interval between primary emergency call and hospital arrival (Call-to-door time[CtD]) is significantly associated with decreased survival rates and unfavorable neurological outcomes in OHCA patients.
- 2) The COVID-19 pandemic has exacerbated the delays in CtD time, further hindering timely treatment and negatively impacting the survival rates and outcomes of OHCA patients.
- 3) The study aims to meticulously explore and quantify the impact of various delayed factors on the prognosis of patients experiencing OHCA, to provide a more comprehensive understanding of their influence.

3. Statistical Analysis Plan

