3.4. Endpoints and covariates

The primary outcome is death from any cause at hospital discharge. Secondary outcomes include death from any cause within 6 and 24 hours, and neurological outcomes assessed using the Glasgow-Pittsburgh Cerebral Performance Category values at hospital discharge. Covariates considered in the analysis include demographics and significant clinical variables such as age and sex.

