3.6. Statistical procedures

All data were presented by the mean with standard deviation for continuous variables and frequency with percentage for categorical variables. The independent two-sample t-test, chi-squared or Fisher's exact test were used to compare differences in continuous or categorical

variables between the two groups. The Cox proportional hazards regression and logistic regression model were used to assess primary and secondary outcomes. The survival probability was estimated using Kaplan–Meier method, and the survival curves were compared between CtD time of <30 min and CtD time of ≥ 30 min groups by the log-rank test. Propensity-score matching and multivariable analyses were also utilized to adjust for confounding variables and assess the impact of CtD time on clinical outcomes. Landmark analysis also was conducted at 24 hours after hospital arrival. Data manipulation and statistical analyses were conducted using SAS version 9.3 (SAS Institute) and R software (version 4.1.1; R Foundation for Statistical Computing, Vienna, Austria). Statistical significance was set at $P < 0.05$. An independent statistician will conduct all statistical analyses to ensure objectivity and accuracy in the interpretation of the data.

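### Arrests after the emergency call are neither excluded nor analysed separately, so entry to the cohort can depend on call-to-door time and the mortality comparison may be distorted

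*Combined protocol and SAP*

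**What the plan says.** Section 2.3 defines eligibility as "Patients of out-of-hospital cardiac arrest were reported to The Korea OHCA Registry". Section 2.4 then removes non-cardiac origin, age under 18, missing data and "Patients who did not receive any CPR"; section 3.3 repeats the same four exclusions. None refers to the timing of the arrest relative to the call or to who witnessed it.

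The exposure in section 2.6 is "a delayed time interval between primary emergency call and hospital arrival (Call-to-door time[CtD", so the clock starts at the call and not at the arrest. The hypothesis is that a longer interval "is significantly associated with decreased survival rates and unfavorable neurological outcomes in OHCA patients". Section 3.4 states that "The primary outcome is death from any cause at hospital discharge", and section 3.6 compares survival "between CtD time of <30 min and CtD time of ≥ 30 min groups".

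For adjustment, section 3.4 gives an open-ended description of the covariates in which only age and sex are named. Section 3.6 plans propensity-score matching and multivariable models without a variable list. It also plans a landmark analysis at 24 hours after hospital arrival. No analysis by arrest timing is described.

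**The concern.** Someone who calls while still alive and collapses later becomes an out-of-hospital case only if the collapse comes before hospital arrival. A patient who would arrest 32 minutes after the call is a case if CtD exceeds 32 minutes. With a shorter CtD the arrest happens in hospital and the patient is never in the cohort. For such patients the exposure helps decide who is observed, which is a selection problem and more than a choice of population. Their CtD also includes minutes before the arrest, so it does not measure delay in treating it.

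Section 1 treats early recognition, CPR and rapid defibrillation as crucial. A crew present at the collapse can supply these at once, so these patients plausibly do better than those found in arrest. If they gather in the ≥30 min group, they work against the hypothesised harm in the primary comparison. Adjusting for age and sex does not remove this. The 24-hour landmark does not either, because it starts after arrival while the selection happens between call and door.

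**Working it through.** **1. The plan's own count.** Section 2.5 expects 76,505 patients, about 42% of 182,508. Subtracting its four exclusion shares gives 182,508 × (1 − 0.28 − 0.005 − 0.25 − 0.04) = 182,508 × 0.425 = 77,566, which is 1.4% above the stated figure. Taking 42% directly gives 76,653. The count is therefore reproduced, within rounding, by the four listed exclusions, and no removal of post-call arrests is listed among them.

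**2. What follows from the definitions alone.** Let T be the time from call to arrest for a patient alive at the call. The patient is an out-of-hospital case only if T < CtD. If T > 30 min, then CtD > 30 min, so the <30 min group cannot contain such a case. Post-call arrests with T ≤ 30 min can fall in either group.

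As an illustration, assume a constant arrest rate of 0.002 per minute among callers still alive. The proportion arresting before the door is 1 − exp(−0.002 × CtD): 4.9% at 25 minutes and 7.7% at 40 minutes. This shows how entry depends on exposure. It does not give the share of each CtD group made up of post-call arrests.

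**3. Effect on the crude odds ratio.** The documents give no survival rates by arrest timing and no shares, so everything here is assumed. Let s be the share of post-call arrests in a CtD group, P the survival of pre-call arrests and A the survival of post-call arrests. Observed survival is S = (1 − s)P + sA. The OR of death is [(1 − S)/S in ≥30 min] ÷ [(1 − S)/S in <30 min].

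Assume P = 10% (<30 min) and 8% (≥30 min). The true OR is (0.92/0.08)/(0.90/0.10) = 1.28. With A equal in both groups:

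| s in <30 / ≥30 min | OR, A = 15% | OR, A = 30% |
|---|---|---|
| 5% / 5% | 1.25 | 1.23 |
| 10% / 10% | 1.23 | 1.20 |
| 5% / 8% | 1.22 | 1.14 |
| 5% / 12% | 1.18 | 1.04 |
| 5% / 15% | 1.15 | 0.97 |
| 10% / 5% | 1.29 | 1.36 |

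Worked example, 5% / 12% with A = 25%:
- <30 min: S = 0.95 × 0.10 + 0.05 × 0.25 = 0.1075
- ≥30 min: S = 0.88 × 0.08 + 0.12 × 0.25 = 0.1004
- OR = (0.8996/0.1004)/(0.8925/0.1075) = 1.08

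**4. Letting post-call survival also fall with CtD.** Take A = 25% (<30 min) and 20% (≥30 min), with s = 5% in the <30 min group. At equal shares the OR stays at 1.28. It is 1.19, 1.11, 1.04 and 0.92 when the ≥30 min share is 10%, 15%, 20% and 30%, with the null reached at about 23%. Across true ORs from 1.12 to 1.48 and the post-call survival rates tried (20%/16%, 25%/20%, 30%/30%), the ≥30 min share that gives a null result runs from about 9.5% to about 39%.

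**The case against.** A reader might infer that the plan keeps post-call arrests and that they hide or reverse the harm of delay. The documents do not support that, for four reasons.

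- **Retention is an inference.** It follows from the absence of an exclusion. Section 3.1 names the registry but does not give its case definition.
- **Reversal is a corner case.** In the table only 5% / 15% with 30% post-call survival falls below 1. Even the OR of 1.08 would not be hidden. With 76,505 patients split evenly (an assumption), the difference is 0.1075 − 0.1004 = 0.0071 with standard error about 0.0022, so z is about 3.2.
- **The net imbalance is not known.** Only arrests later than 30 minutes are placed by construction. A patient who collapses with a crew at hand could reach hospital sooner than one resuscitated on scene. If post-call arrests were more common in the <30 min group, harm would be exaggerated (last row of the table).
- **Part of the dilution is an assumption.** At equal shares it arises because post-call survival was set the same in both groups. It disappears in step 4.

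These points stand, and they limit the claim about direction and size. It is also true that the open covariate description could cover witness status. Nothing commits the analysis to it, however, and no adjustment can supply a <30 min comparator for arrests after 30 minutes. The selection mechanism is untouched by the objections, provided the registry holds such cases.

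**Conclusion.** The gap is real, and its consequence is conditional. The plan starts the exposure clock at the call, sets no condition on when the arrest occurred, and has no analysis that separates post-call arrests. If the registry contains them, entry depends on CtD for those patients.

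The likelier effect is attenuation of the association between CtD and death. Masking or reversal needs a large imbalance in shares, a small true effect, or much better survival after a post-call arrest. On the assumed rates with equal post-call survival in both groups, a true OR of 1.28 appears as about 0.97 to 1.25 when post-call arrests are at least as common in the ≥30 min group, and as about 1.29 to 1.36 at 10% versus 5%. These are crude odds ratios on assumed inputs and do not predict this study's result. The point is worth acting on because the primary comparison is exposed and the remedy is cheap.

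**What to change.** State in sections 2.4 and 3.3 that the primary CtD comparison is restricted to arrests that occurred before the emergency call, with EMS-witnessed and in-transport arrests excluded. Prespecify the full cohort as a sensitivity analysis, and report the number of post-call arrests in each CtD group. If the registry already leaves these cases out, one sentence saying so settles the point.

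The cost is one eligibility line, one extra run on existing data and one table row. There are three downsides.

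- **Smaller cohort.** If post-call arrests were 5%, 10% or 15% of 76,505 (assumed), about 72,680, 68,855 or 65,029 patients would remain.
- **Narrower conclusion.** It would apply only to arrests before the call. Stratifying by arrest timing would keep the cohort whole, but would leave arrests after 30 minutes without a comparator.
- **Reliance on a registry field.** EMS-witnessed status or arrest time must be recorded. Witness status alone would miss a collapse between the call and the crew's arrival, so arrest time is preferable where it exists.

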2.5. Sample size calculation

Between 2016 and 2021, 182,508 patients have been included in the Korea OHCA registry. Of these about 28% have been non-cardiac origin, about 0.5% have been under 18 years of age, about 25% has been did not receive any CPR, and about 4% has been missing data. Thus we assume that about 42% i.e. 76,505 patients will fulfil the inclusion criteria without exclusion criteria

2.6. Hypothesis

- 1) The study hypothesizes that a delayed time interval between primary emergency call and hospital arrival (Call-to-door time[CtD]) is significantly associated with decreased survival rates and unfavorable neurological outcomes in OHCA patients.
- 2) The COVID-19 pandemic has exacerbated the delays in CtD time, further hindering timely treatment and negatively impacting the survival rates and outcomes of OHCA patients.
- 3) The study aims to meticulously explore and quantify the impact of various delayed factors on the prognosis of patients experiencing OHCA, to provide a more comprehensive understanding of their influence.

3. Statistical Analysis Plan

3.1. Data source

The data for this study was sourced from the Korea OHCA Registry, a collaborative database established by the Korea Centers for Disease Control and Prevention and the central fire services under the Korean government leadership.

3.2. Analysis objectives

The primary objective of the analysis is to investigate the impact of call-to-door (CtD) time on the clinical outcomes of patients experiencing OHCA. The study aims to discern the influence of delayed hospital arrival on survival rates and neurological outcomes, considering the potential exacerbations brought about by the COVID-19 pandemic.

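### Call-to-door time contains on-scene time and is never split, so if scene time depends on response to resuscitation, its association with death cannot be read as the impact of delay

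*Combined protocol and SAP*

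**What the plan says.** Hypothesis 1 in Section 2.6 defines the exposure and words the claim as an association: "a delayed time interval between primary emergency call and hospital arrival (Call-to-door time[CtD]) is significantly associated with decreased survival rates". The other statements of purpose go further. The Background announces a study of the "impact of time from call to hospital arrival (CtD time) on clinical outcomes in patients experiencing OHCA". Section 3.2 says: "The study aims to discern the influence of delayed hospital arrival on survival rates and neurological outcomes". Section 3.6 uses matching and multivariable models to "adjust for confounding variables and assess the impact of CtD time on clinical outcomes". Hypothesis 2 says the pandemic has "exacerbated the delays in CtD time, further hindering timely treatment and negatively impacting the survival rates and outcomes of OHCA patients".

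On the form of the exposure, Section 3.6 says the "survival curves were compared between CtD time of <30 min and CtD time of ≥ 30 min groups by the log-rank test". It does not say how CtD enters the Cox and logistic models. On adjustment, Section 3.4 says: "Covariates considered in the analysis include demographics and significant clinical variables such as age and sex". That list is open: return of circulation is neither named nor ruled out.

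Hypothesis 3 promises to "explore and quantify the impact of various delayed factors on the prognosis of patients experiencing OHCA", but does not define these factors, and no analysis in Section 3.6 is tied to it. No section mentions on-scene time or divides CtD into parts.

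**The concern.** CtD is the sum of the time until the crew arrives, the time on scene and the transport time. The middle part elapses while resuscitation is under way. If its length depends on whether the patient responds, part of the exposure is a consequence of early prognosis. Long and short CtD groups would then differ partly in their mix of responders and non-responders.

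Reading the result as the impact of delay needs the opposite assumption, that scene time is unrelated to response. The plan neither states nor tests this. Variables fixed before the call, such as age and sex, cannot fully stand in for response. The landmark at 24 hours after arrival does not help, because it concerns follow-up after the exposure has ended.

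At stake is the main conclusion: an association produced by who responded on scene could be credited to delay, or a harmful delay could be hidden behind it.

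**Working it through.** **1. The plan's own figure.** Section 2.5 gives 182,508 registry patients and exclusion shares of 28%, 0.5%, 25% and 4%, which add to 57.5%. Then (1 - 0.575) × 182,508 = 77,566, within 1.4% of the stated 76,505 (41.9% of the total). N = 76,505 is used below, with alpha 0.05 from Section 3.6. Its sidedness is not stated; two-sided is assumed.

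**2. Assumed inputs for a worked example** (none is in the documents). Response plus transport time: mean 17 min, SD 5. On-scene time: mean 13 min, SD 4, shifted by s minutes in patients whose circulation returns before hospital. Return of circulation: 10%. Survival: 50% with it, 2% without. No time interval affects death.

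**3. Calculation, s = -5.** CtD has mean 30 and SD √(25 + 16) = 6.40 without return of circulation, so P(CtD ≥ 30) = 0.500. With return, the mean is 25 and P(CtD ≥ 30) = 1 - Φ(5/6.40) = 0.217.

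- Dead, ≥30: 0.1×0.5×0.217 + 0.9×0.98×0.5 = 0.4519
- Alive, ≥30: 0.1×0.5×0.217 + 0.9×0.02×0.5 = 0.0199
- Dead, <30: 0.1×0.5×0.783 + 0.9×0.98×0.5 = 0.4801
- Alive, <30: 0.1×0.5×0.783 + 0.9×0.02×0.5 = 0.0481

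OR = (0.4519 × 0.0481)/(0.0199 × 0.4801) = 2.28. With s = +5 the two columns swap and OR = 1/2.28 = 0.44.

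The adjusted row comes from logistic models on simulated cohorts of 76,505 in which age and sex predict both return of circulation and survival.

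| Shift s (min) | -5 | -2 | 0 | +2 | +5 |
|---|---|---|---|---|---|
| OR, unadjusted | 2.28 | 1.40 | 1.00 | 0.71 | 0.44 |
| OR, adjusted for age and sex | 2.26 | 1.40 | 0.99 | 0.72 | 0.44 |

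**4. Wider grid, still with no delay effect.** Gamma response time (mean 8 min) and transport time (mean 9 min), scene limit 8-16 min (fixed or SD 4), 8% or 15% return of circulation, mortality 95% without it and 45% with it.

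- Responders leave at return of circulation: OR 1.25-3.5 (up to 4.9 if returns cluster early).
- Responders stay 5 min longer than others: OR 0.33-0.68.
- No dependence: OR 1.00.

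With 80% mortality after return of circulation, the first two ranges become 1.10-2.15 (early-clustered returns included) and 0.56-0.85. None of these ranges bounds the bias.

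**5. Significance.** Under the step 2 inputs with s = 0, the cells are 0.466, 0.034, 0.466 and 0.034. SE(log OR) = √[(2/0.466 + 2/0.034)/76,505] = 0.0287, so the smallest significant OR is exp(1.96 × 0.0287) = 1.06. Over the assumed mortalities and shares at or above 30 min it is about 1.04-1.10. This uses all 76,505 patients unmatched; matching may use fewer, and the threshold would then be further from 1.

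**6. Can adjustment solve it?** A pre-call score predicting return of circulation with AUC 0.75-0.85 still left ORs of 1.28-2.66 (leave sooner) and 0.46-0.72 (stay longer). Adjusting for return of circulation itself gave 0.97-1.03 when there was no delay effect. But when later crew arrival was made truly harmful by lowering the chance of return (OR 1.10-1.16 per 5 min), the same adjustment reduced that effect to 0.99-1.02. It can therefore remove a true delay effect together with the artefact.

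**The case against.** The strongest reply is that everything rests on facts outside the documents. No section describes crew behaviour, scene times, return of circulation or mortality, and a range running from 0.33 through 1.00 to 3.5 shows only that bias is possible. This stands. A reader might infer that the planned result will be biased, or will have the wrong sign; the documents do not support that, because they give neither the direction nor the size of any dependence.

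Second, a reader might infer that the 30-minute split is the only planned contrast. Section 3.6 names it only for the Kaplan-Meier and log-rank comparison, so the odds ratios above apply to one reading of the plan. The point does not depend on the split, since any form of total CtD contains scene time.

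Third, the open covariate list could include return of circulation. That is possible, but such adjustment may act on a step between delay and death and is not a clean remedy.

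Fourth, this is openly a registry cohort and hypothesis 1 already speaks of association. That narrows the wording complaint. It does not remove it, because Sections 1, 3.2 and 3.6 use causal terms and no section limits that reading.

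Finally, that hypothesis 3 is about time components is an inference; its delay factors are undefined.

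**Conclusion.** The concern holds in conditional form. Total CtD mixes intervals that may relate to prognosis in different ways, and the plan reads its association with death as impact without the assumption this requires. If scene time depends on response and response predicts survival, an association of either sign can arise with no delay effect: illustratively an OR of about 1.25-3.5 or 0.33-0.68 for the binary split, and 1.00 with no dependence. Adjustment for age and sex does not remove it.

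Because an OR of about 1.04-1.10 would reach P < 0.05 under the assumed mortality and exposure shares in the full unmatched cohort, a significant result would not by itself separate delay from response. It does not follow that significance is assured: if the dependence is weak or absent, so is the artefact. This is a worthwhile, inexpensive improvement to the plan; it does not show that total CtD is an invalid exposure.

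**What to change.** Keep total CtD as the declared exposure and make these changes.

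- **Section 3.6:** prespecify a supplementary analysis of call-to-EMS-arrival, on-scene and scene-to-door intervals, once it is confirmed that the registry holds the timestamps. Fit call-to-EMS-arrival without the later intervals, because they come after it. Note that it can still be confounded, for example by location, and that scene-to-door time may also depend on response.
- **Section 3.6:** label any adjustment for, or stratification by, return of circulation as exploratory, because it may lie on the path from delay to death.
- **Sections 3.2 and 3.6:** describe the total-CtD result as an association with total pre-hospital time, in line with hypothesis 1.
- **Section 2.6:** say whether the delay factors in hypothesis 3 include time components. If so, the supplementary analysis serves that hypothesis.

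The cost is SAP wording, a few extra models and some patients lost from the component models through missing timestamps. The documents list no registry fields; if the timestamps are unavailable, only the change to association wording applies.

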3.3. Analysis sets

The study included patients selected from OHCA patients enrolled between January 2016 and December 2021. Exclusions were made based on criteria such as non-cardiac origin of arrest, age below 18, absence of CPR, and missing data.

